#### 8. Efficacy Analysis

			Main Estin		
	Estimand Description	Analysis Set	Intercurrent Events	Analysis Model/Method	Sensitivity and Supplementary Analyses
Estimand 1a	This estimand is intended to provide a population-level estimate of the anti-psoriatic effect of DC-806 versus Placebo on a binary composite responder endpoint (PASI-75) at Week 12 without the benefit of other background anti- psoriasis therapy regardless of the use of topical bland moisturizers or emollients, or bland shampoos, as needed and regardless of treatment interruption.	FAS	Receiving any prohibited medication* or discontinuing the treatment due to related adverse event or requirement for prohibited medication* → Composite strategy Discontinuing the treatment due to any other reason è Hypothetical strategy Treatment interruption è Treatment policy	Either Fisher's exact or Chi- squared. Participants with no Week 12 data (observed or imputed) will be considered as non-responder.	
Estimand 1b	This estimand is intended to provide a population-level estimate of the anti-psoriatic effect of DC-806 versus Placebo on a binary composite responder endpoint (PASI-75) at Week 12 without the benefit of other background anti- psoriasis therapy regardless of the use of topical bland moisturizers or emollients, or bland shampoos, as needed and regardless of treatment interruption.	FAS	Receiving any prohibited medication* or discontinuing the treatment due to related adverse event or requirement for prohibited medication* → Composite strategy Discontinuing the treatment due to any other reason → Hypothetical strategy Treatment interruption è Treatment policy	
 
Participants with no Week 12 data (observed or imputed) will be considered as non-responder.
 
b) A logistic regression model will be performed with PASI-
 
	

				75 at Week 12 as binary	
				response and treatment,	
				baseline PASI score (as a	
				continuous covariate) as	
				covariates. The following	
				additional covariates will be	
				tested in the model using	
				backward elimination with a	
				significance level of 0.2 to	
				retain the covariates in the	
				model: age, BMI and weight as	
				continuous covariates, sex,	
				previous biologic therapy and	
				geographic region as discrete	
				covariates. At the very least,	
				previous biologic therapy and	
				geographic region will be	
				retained in the model. The	
				conditional odds ratio, with	
				Placebo as reference group,	

Estimand 4a / 4b	This estimand is intended to provide a population-level estimate of the anti-psoriatic effect of DC-806 versus Placebo on a binary composite responder endpoint (sPGA score of 0 (clear) or 1 (almost clear) with $\geq 2$ grade improvement from Baseline) at Week 12 without the benefit of other background anti-psoriasis therapy regardless of the use of topical bland moisturizers or emollients, or bland shampoos, as needed and regardless of treatment interruption.	Same as E	stimand 1a/1b with sPGA score of	of 0 (clear) or 1 (almost clear) with $\ge 2$	grade improvement from Baseline.
Estimand 5a, 5b, 5c, 5d	This estimand is intended to provide a population-level estimate of the anti-psoriatic effect of DC-806 versus Placebo on a binary composite responder endpoint (PASI-50) at scheduled timepoints up to Week 12 without the benefit of other background anti-psoriasis therapy regardless of the use of topical bland moisturizers or emollients, or bland shampoos,	FAS	Receiving any prohibited medication* or discontinuing the treatment due to related adverse event or requirement for prohibited medication* → Composite strategy Discontinuing the treatment due to any other reason è Hypothetical strategy Treatment interruption è Treatment policy	Missing values at each visit will be imputed as non-responder. Generalized estimating equation (GEE) with PASI-50 (a)/PASI- 75(b)/PASI-90(c)/PASI-100(d) up to Week 12 as binary response and treatment, visit, baseline PASI score (as a continuous covariate) as covariates and a treatment by visit interaction. The following additional covariates will be tested in the model using backward elimination with a significance	

	as needed and regardless of treatment interruption.			level of 0.2 to retain the covariates in the model: age, BMI and weight as continuous covariates, sex, previous biologic therapy and geographic region as discrete covariates. At the very least, previous biologic therapy and geographic region will be retained in the model. The conditional odds ratio, with Placebo as reference group, and their corresponding 2-sided 95% CI will be presented.			
Estimand 6	This estimand is intended to provide a population-level estimate of the anti-psoriatic effect of DC-806 versus Placebo on a binary composite responder endpoint (sPGA score of 0 [clear] or 1 [almost clear]) at scheduled timepoints up to Week 12 without the benefit of other background anti-psoriasis therapy regardless of the use of topical bland moisturizers or emollients, or bland shampoos, as needed and regardless of treatment interruption.	Same as Estimand 5 with sPGA score of 0 (clear) or 1 (almost clear).					
Estimand 7a	This estimand is intended to provide a population-level estimate of the anti-psoriatic effect of DC-806 on a continuous endpoint (PASI) as though no discontinuations of treatment for any reason occur, as though no intake of prohibited medications* and	FAS	Receiving any prohibited medication* or discontinuing the treatment due to any reason → Hypothetical strategy Treatment interruption è Treatment policy	MMRM on PASI percentage change from baseline with treatment, visit and PASI score baseline, previous biologic therapy and geographic region as covariates and a treatment by visit interaction. The following additional covariates will be tested in the model using backward elimination with a significance level of 0.2 to retain	CC		

	regardless of treatment interruption.			the covariates in the model: age, BMI and weight as continuous covariates, sex, as discrete covariate.	
Estimand 7b	This estimand is intended to provide a population-level estimate of the anti-psoriatic effect of DC-806 on a continuous endpoint (PASI) as though no discontinuations of treatment for any reason occur, as though no intake of prohibited medications* and regardless of treatment interruption.	FAS	Receiving any prohibited medication* or discontinuing the treatment due to any reason è Hypothetical strategy Treatment interruption è Treatment policy	MMRM on PASI absolute change from baseline with treatment, visit and PASI score baseline, previous biologic therapy and geographic region as covariates and a treatment by visit interaction. The following additional covariates will be tested in the model using backward elimination with a significance level of 0.2 to retain the covariates in the model: age, BMI and weight as continuous covariates, sex, as discrete covariate.	CC
Estimand 8a / 8b	This estimand is intended to provide a population-level estimate of the anti-psoriatic effect of DC-806 on a continuous endpoint (BSA) as though no discontinuations of treatment for any reason occur, as though no intake of prohibited medications* and regardless of treatment interruption.	Same as E	Estimand 7a/7b with BSA percent	age change and absolute change from	baseline.

\* Prohibited medications are the medications used for treating psoriasis and also having an impact on the efficacy assessment. Note: previous biologic therapy and geographic region used as covariates will be taken from IRT

# 8.1. Primary Efficacy Endpoint: Proportion of Participants achieving PASI-75 at Week 12 (Estimands 1a and 1b)

The primary endpoint for estimands 1a and 1b is the proportion of participants achieving at least 75% reduction in PASI score from baseline to Week 12 and is defined as PASI-75 as follows:

Percentage change from baseline in PASI score at Week 12 is defined as:

% change of PASI = 100 \* (PASI score at Week 12 - PASI score at Baseline) / PASI score at Baseline.

Thus, PASI-75 at Week 12 is defined as a binary variable such that: PASI-75 = Responder if % change of PASI  $\leq$  -75%; Non-responder, otherwise.

The number and proportion of participants achieving PASI-75 at Week 12 with corresponding 95% CI will be presented by treatment group for the FAS.

#### 8.1.1. Estimand 1a

#### 8.1.1.1. Main Analysis Approach

A participant receiving any prohibited medication or discontinuing the treatment due to related adverse event or requirement for prohibited medication prior to Week 12 visit will be considered as a non-responder (Composite strategy). If a participant discontinued treatment for reasons other than related adverse event or requirement for prohibited medication, PASI scores after the treatment discontinuation date will be set to missing (Hypothetical strategy). If a participant experienced any treatment interruption, PASI score reported after the treatment interruption will be used as reported (Treatment policy).

Participants without Week 12 PASI score (either due to hypothetical strategy implementation or missed visit) will be considered as non-responder.

A 2-sided, 2-sample Fisher's exact or Chi-squared test will be performed to assess a difference between active treatment groups (DC-806) versus Placebo in PASI-75 at Week 12 for the following comparisons on the FAS:

#### Comparison 1

H0: PASI-75 at Week 12  $_{DC-806\ 800mg}$  = PASI-75 at Week 12  $_{Placebo}$ H1: PASI-75 at Week 12  $_{DC-806\ 800mg} \neq$  PASI-75 at Week 12  $_{Placebo}$ 

#### Comparison 2

H0: PASI-75 at Week 12  $_{DC-806\ 600mg}$  = PASI-75 at Week 12  $_{Placebo}$ H1: PASI-75 at Week 12  $_{DC-806\ 600mg} \neq$  PASI-75 at Week 12  $_{Placebo}$ 

#### Comparison 3

H0: PASI-75 at Week 12  $_{DC-806 400mg}$  = PASI-75 at Week 12  $_{Placebo}$ 

H1: PASI-75 at Week 12  $_{DC-806 \ 400 mg} \neq$  PASI-75 at Week 12  $_{Placebo}$ 

#### Comparison 4

H0: PASI-75 at Week 12  $_{DC-806\ 200mg}$  = PASI-75 at Week 12  $_{Placebo}$ H1: PASI-75 at Week 12  $_{DC-806\ 200mg} \neq$  PASI-75 at Week 12  $_{Placebo}$ 

The number and percentage of participants who are defined as PASI-75 responder will be presented by treatment group. The p-value and unconditional odds ratio with its corresponding 95% CI will be presented in the active treatment group compared to the placebo group. All comparisons will be performed in a prespecified hierarchical procedure starting from the highest dose regimen to the lowest dose regimen.

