3.0 STUDY OBJECTIVES, ENDPOINTS, AND ESTIMANDS

Objectives	Endpoints	Estimands
Primary		
To compare the efficacy of multiple doses of DC-806 versus placebo in adult participants with moderate to severe plaque psoriasis	Proportion of participants achieving PASI-75 at Week 12	Estimand 1a: This estimand is intended to provide a population-level estimate of the anti-psoriatic effect of DC-806 versus placebo on a binary composite responder endpoint (PASI-75) at Week 12 without the benefit of other background anti-psoriasis therapy, regardless of the use of topical bland moisturizers, emollients, or bland shampoos as needed, and regardless of treatment interruption Target Population: Participants with moderate to severe plaque psoriasis • Treatment Conditions: Each of 4 dosing regimens of DC-806 (CCI) compared to placebo administered orally 4 tablets each morning and 4 tablets each evening for 12 weeks irrespective of interruptions and on top of use of topical bland moisturizers, emollients, or bland shampoos as needed • Variable: Responder is defined as achieving ≥75% reduction in PASI-75 at Week 12 without the use of other background anti-psoriasis therapy. Non-responder is defined as not achieving PASI-75 at Week 12 or receiving any prohibited medication ^a (including an alternative therapy for psoriasis and interacting drugs), or discontinuing the treatment due to related AE or requirement for prohibited medication ^a (Composite strategy). • Strategies for Intercurrent Events: As though no discontinuations of treatment due to any other reasons occur (Hypothetical strategy) • Population-Level Summary: Difference in the response rates at Week 12 Estimand 1b: As above but with odds ratio as population-level summary

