#### 2.1. Primary Objectives, Endpoints, and Estimands

The primary objectives, corresponding endpoints and estimands are displayed in the below table:

Primary Objectives	Endpoints	Estimands
Primary Objectives To compare the efficacy of multiple doses of DC-806 versus placebo in adult participants with moderate to severe plaque psoriasis	Endpoints Proportion of participants achieving Psoriasis Area of Severity Index score (PASI-75) at Week 12	Estimands Estimand 1a: This estimand is intended to provide a population-level estimate of the anti- psoriatic effect of DC-806 versus Placebo on a binary composite responder endpoint (PASI-75) at Week 12 without the benefit of other background anti-psoriasis therapy, regardless of the use of topical bland moisturizers, or emollients, or bland shampoos, as needed, and regardless of treatment interruption Target Population: Participants with moderate to severe plaque psoriasis Treatment Conditions: Each of 4 dosing regimens of DC-806 (CCI ) compared to placebo administered orally 4 tablets each morning and 4 tablets each evening for 12 weeks irrespective of interruptions, and on top
		
 
morning and 4 tablets each evening for 12 weeks irrespective of interruptions, and on top of use of topical bland moisturizers. or emollients, or bland shampoos, as needed
 
Variable: Responder is defined as achieving ≥75% reduction in Psoriasis Area of Severity Index score (PASI-75) at Week 12 without the use of other background antipsoriasis therapy. Non-responder is defined as not achieving PASI-75 at Week 12 or receiving any prohibited medication* (including an alternative therapy for psoriasis and interacting drugs), or discontinuing the treatment due to related AE or requirement for prohibited medication*. (Composite strategy)
 
Strategies for Intercurrent Events: As though no discontinuations of treatment due to any other reasons occur. (Hypothetical strategy)
 
Population-Level Summary: Difference in the response rates at Week 12
 
Estimand 1b: As above but with odds ratio as population-level summary
 

To compare the safety and tolerability	Incidence proportion of	Estimand 2a: This estimand is intended to provide a population-level estimate of the
of multiple doses of DC-806 versus	treatment-emergent	incidence proportion of treatment-emergent adverse events (TEAEs)
placebo in adult participants with	adverse events (TEAEs),	

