#### 8.2.1.1.4. Additional Supplementary Analyses

A Cochran-Armitage trend test will be conducted to assess a positive trend between DC-806 dose regimens and PASI-75 at Week 12. The two-sided p-value test against either an increasing or decreasing alternative will be provided.

A participant receiving any prohibited medication or discontinuing the treatment due to related adverse event or requirement for prohibited medication prior to Week 12 visit or participants with missing Week 12 PASI score will be considered as a non-responder.

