#### 8.2.2.1. Main Analysis Approach

Similar methods and intercurrent event strategies as applied in the main analysis provided for Estimand 1a/1b analysis will be used to evaluate proportion of participants achieving a sPGA score of 0 (clear) or 1 (almost clear) with  $\geq 2$  grade improvement from Baseline at Week 12 on FAS. (see Sections 8.1.1.1 and 8.1.2.1).

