# 8.2.3. Proportion of participants achieving ≥50%, ≥75%, ≥90%, and 100% reduction in PASI score (PASI-50, PASI-75, PASI-90, and PASI-100, respectively) at scheduled timepoints (Estimands 5a, 5b, 5c, 5d)

#### 8.2.3.1. Main Analysis Approach

A participant receiving any prohibited medication or discontinuing the treatment due to related adverse event or requirement for prohibited medication will be considered as a non-responder at scheduled timepoints following the event (Composite strategy). If a participant discontinued treatment for reasons other than related adverse event or requirement for prohibited medication, PASI scores reported after the treatment discontinuation date will be treated as missing (Hypothetical strategy). If a participant experienced any treatment interruption, PASI score reported after the treatment interruption will be used as reported (Treatment policy).

Participants without PASI score at each scheduled visit (either due to hypothetical strategy implementation or missed visit) will be considered as non-responder.

The following analyses will be performed using generalized estimating equation (GEE) as an extension of the logistic regression model with treatment, visit and baseline PASI score (as a continuous covariate) as covariates and a treatment by visit interaction. The following additional covariates will be tested in the model using backward elimination with a significance level of 0.2 to retain the covariates in the model: age, BMI and weight as continuous covariates, sex, previous biologic therapy (Yes/No) (as per IRT) and geographic region (North America/Western Europe vs. Eastern Europe) (as per IRT). At the very least, previous biologic therapy and geographic region will be retained in the model. Of note, visits from the earliest timepoint with at least one responder will be included in the model. e.g. if the first responder is on Day 15, all GEE models will include visits from Day 15.

- Participants achieving ≥50% reduction in PASI score (PASI-50) at scheduled timepoints up to Week 12 by treatment group for the FAS. (Estimand 5a)
- Participants achieving ≥75% reduction in PASI score (PASI-75) at scheduled timepoints up to Week 12 by treatment group for the FAS. (Estimand 5b)
- Participants achieving ≥90% reduction in PASI score (PASI-90) at scheduled timepoints up to Week 12 by treatment group for the FAS. (Estimand 5c)

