# 8.2.4.1. Main Analysis Approach

Similar methods and intercurrent event strategies as applied in the main analysis provided for Estimand 5 analysis will be used to evaluate proportion of participants achieving a sPGA score of 0 (clear) or 1 (almost clear) with  $\geq$ 2 grade improvement from Baseline at scheduled timepoints up to Week 12 on FAS (see Section 8.2.3.1).

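### Binary estimands: stops for other reasons are labelled hypothetical, but the main analysis scores them as failures, which is a composite strategy

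*SAP*

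**What the plan says.** The Estimand 1a entry in Protocol Section 3.0 separates two kinds of treatment discontinuation. A stop for a related adverse event, or because prohibited medication is required, makes the participant a non-responder (composite strategy). For the rest, the strategy reads "As though no discontinuations of treatment due to any other reasons occur (Hypothetical strategy". SAP Section 2.1 repeats this: "As though no discontinuations of treatment due to any other reasons occur. (Hypothetical strategy". Estimands 3 to 6 carry the same split.

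SAP 8.1.1.1 implements the second strategy in two steps. PASI scores after an other-reason stop are set to missing. Then: "Participants without Week 12 PASI score (either due to hypothetical strategy implementation or missed visit) will be considered as non-responder".

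The same sentence appears for Estimands 1b (8.1.2.1), 3a (8.2.1.1.1) and 3b (8.2.1.2.1). For Estimands 5a to 5d, 8.2.3.1 says "Participants without PASI score at each scheduled visit (either due to hypothetical strategy implementation or missed visit) will be considered as non-responder". Estimand 4 inherits the rule in 8.2.2.1 ("Similar methods and intercurrent event strategies as applied in the main analysis provided for Estimand 1a/1b analysis will be used") and Estimand 6 in 8.2.4.1 ("Similar methods and intercurrent event strategies as applied in the main analysis provided for Estimand 5 analysis will be used"). The trend test in 8.2.1.1.4 also scores missing results as failures: "participants with missing Week 12 PASI score will be considered as a non-responder".

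The table in SAP Section 8 uses slightly different words, "Participants with no Week 12 data (observed or imputed) will be considered as non-responder", but the visible main-analysis text contains no imputation step before the non-responder rule. SAP Section 12 records no change from the planned analysis.

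**The concern.** A hypothetical strategy asks what the outcome would have been had the participant not stopped. Scoring the stop as failure answers a different question, and the SAP itself calls that scoring composite when it applies it to related adverse events and prohibited medication. Once both kinds of stop are scored as failure, the distinction drawn in the estimand has no effect on the estimate.

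The SAP handles the label differently elsewhere. Estimand 7, and Estimand 8 by reference, also use a hypothetical strategy and set later data to missing, but analyse by MMRM under a missing-at-random assumption (8.2.5.1.1), which fits the label.

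At stake is what the primary PASI-75 result is said to estimate. A report that follows the estimand table would describe an effect free of other-reason stops when each of them has been counted as a failure. In a dose-ranging trial this also affects the dose-versus-dose comparisons: unequal discontinuation alone could make two equally effective doses look different.

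**Working it through.** **Passages side by side (binary estimands)**

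| Event | Stated strategy | Value in the main analysis |
|---|---|---|
| Prohibited medication; stop for related AE or need for prohibited medication | Composite | Non-responder |
| Stop for any other reason | Hypothetical | Set to missing, then non-responder |
| Treatment interruption | Treatment policy | PASI used as reported |

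The first two rows end at the same value.

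**Size**

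There is no figure in the plan to reproduce. SAP 4.2 gives about 225 participants in five arms of 45 (5 × 45 = 225), with no visible power, response rates or dropout. All rates below are therefore assumptions.

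Notation:
- pA, pP: response rates in the active and placebo arms had no other-reason stop occurred.
- dA, dP: proportions stopping for other reasons.
- f: would-be response rate among those who stop, relative to their arm's rate. f = 1 means stopping is unrelated to response; f = 0 means all who stop would have failed.

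Hypothetical difference: pA − pP.

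Rates under the SAP rule: a = pA(1 − f·dA) and b = pP(1 − f·dP).

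Difference under the SAP rule: a − b = (pA − pP) − f(pA·dA − pP·dP).

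Odds ratio under the SAP rule: [a/(1 − a)] / [b/(1 − b)].

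Example with pA = 0.60, pP = 0.10, dA = 0.15, dP = 0.05, f = 1:
- a = 0.60 × 0.85 = 0.51 and b = 0.10 × 0.95 = 0.095
- difference = 0.415
- odds ratio = (0.51/0.49)/(0.095/0.905) = 9.92

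| pA / pP | dA / dP | Difference in points, f = 1 / 0.5 / 0 | Odds ratio, f = 1 / 0.5 / 0 |
|---|---|---|---|
| 60% / 10% | 10% / 10% | 45.0 / 47.5 / 50.0 | 11.87 / 12.63 / 13.5 |
| 60% / 10% | 15% / 5% | 41.5 / 45.75 / 50.0 | 9.92 / 11.54 / 13.5 |
| 30% / 10% | 5% / 20% | 20.5 / 20.25 / 20.0 | 4.58 / 4.18 / 3.86 |
| 30% / 10% | 5% / 15% | 20.0 / 20.0 / 20.0 | 4.29 / 4.06 / 3.86 |

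The f = 0 value in each cell is the hypothetical target.

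**Direction.** With the same f > 0 in both arms, the difference is inflated only if pP·dP > pA·dA. At 60% and 10% that needs dP more than six times dA; at 30% and 10%, more than three times. Otherwise it is attenuated or, at equality, unchanged. The odds ratio can inflate sooner, as the last row shows.

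**Scale.** The standard error of a 60% versus 10% difference at 45 per arm is √(0.6 × 0.4/45 + 0.1 × 0.9/45) = 0.0856, or 8.56 points. The 5-point shift in the first row is 5/8.56 ≈ 0.6 standard errors.

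**Dose against dose (Estimand 3).** Take two doses that both have a true rate of 50%, with 5% and 20% stopping and f = 1. The analysed rates are 0.50 × 0.95 = 0.475 and 0.50 × 0.80 = 0.40. The rule shows a difference of 7.5 points and an odds ratio of (0.475/0.525)/(0.40/0.60) = 1.36, where the hypothetical contrast is zero.

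**The case against.** The strongest defence is that the SAP takes two separate steps. The intercurrent-event step sets scores to missing under the hypothetical strategy; the missing-data step, which also covers missed visits, makes a worst-case assumption about the unobserved outcome. On that reading the label is right and the assumption merely strong. This is coherent only at f = 0, where everyone who stops would have failed. Neither document states that assumption, and it still leaves the split between related-AE and other-reason stops with no effect on the result.

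Several other points stand, as limits rather than rebuttals:
- The SAP contents list sensitivity and supplementary sections for these estimands whose text is not visible, and the table wording on imputed data hints that an imputation analysis may exist. That could meet part of the remedy, but it cannot alter the main rule.
- Protocol 7.2 expects withdrawal from the study to be uncommon. This is indirect evidence on stopping treatment, but at 5% in both arms (60% versus 10%, f = 1) the difference would be 57.0 − 9.5 = 47.5 points, a shift of 2.5/8.56 ≈ 0.3 standard errors.
- SAP 8.1.1.1 reports an odds ratio and p-value; the difference, strata-adjusted, appears under 8.1.2.1. The rule feeds both.
- Estimand 7 covers a different set of events on a continuous endpoint, so its different model is not itself an error.
- Non-responder scoring is prespecified and openly stated, and Protocol 9.3 calls the analysis descriptive and exploratory.

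**Conclusion.** The concern holds. For Estimands 1, 3, 4, 5 and 6 the visible main analysis is a composite-strategy estimator for every treatment stop that precedes the assessment, while both documents label part of those stops hypothetical. That much follows from the text and needs no assumption.

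The numerical consequence does rest on assumed rates. In the placebo comparisons illustrated, the difference ranges from 8.5 points too small to 0.5 points too large; the odds ratio can err in either direction. With few other-reason stops, or if those who stop would mostly have failed, the gap is small. The non-responder rule is a legitimate main analysis. What needs correcting is the description of what it estimates, and this should be fixed because it concerns the primary endpoint.

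**What to change.** 1. Keep non-responder scoring as the main analysis.
2. For Estimands 1 and 3 to 6, change the strategy for other-reason discontinuation from hypothetical to composite in SAP Sections 2.1, 2.2 and 8 and in the Protocol Section 3.0 table. Alternatively, leave the protocol as it is and record the departure in SAP Section 12. Missed visits without discontinuation are a missing-data matter and can keep their own rule.
3. Unless a section not visible here already contains one, add a supplementary analysis of the hypothetical effect: multiple imputation of Week 12 PASI under missing at random, by arm, from Baseline and Days 8, 15, 29 and 57, then dichotomised at a 75% reduction. Related-AE and prohibited-medication events stay as non-responders.
4. Align one sentence. Protocol 9.5 says missing dermatology data are not imputed, whereas the SAP Section 8 table imputes them as non-response for Estimand 5. Protocol 9.5 defers to the SAP for detail, so this is wording only.

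The cost is text edits and at most one imputation program. No new data are needed and the main numerical result does not change. Editing the protocol table means an amendment, which would need ethics approval if judged substantial; the Section 12 route avoids amending the estimand table.
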